5.3. Lifestyle Considerations

No restrictions are required.

5.4. Screen Failures

Screen failures are defined as participants who consent to participate in the clinical study but are not subsequently randomly assigned to study treatment.

Tests with results that fail eligibility requirements may be repeated once during screening if the investigator believes that the participant would be eligible if retested. Additionally, a participant who fails screening may repeat the screening process 1 time if the investigator believes that there has been a change in eligibility status. Participants who are rescreened must reconsent and be assigned a new participant number.

5.5. Replacement of Participants

No participants will be replaced at any time during this study.

6. STUDY TREATMENT

6.1. Study Treatment Administered

Information regarding study drug and administration is provided in [Table 6](#). Participants will record study drug administration in a daily electronic diary.

Table 6: Study Treatment Information

	Study Treatment 1	Study Treatment 2
Study treatment name:	INCB054707	Matching placebo
Dosage formulation:	Tablet	Tablet
Unit dose strength(s)/ Dosage level(s):	[REDACTED] [REDACTED] [REDACTED]	[REDACTED]
Route of administration:	Oral	
Administration instructions:	INCB054707 and matching placebo will be taken orally once daily with water without regard to food, preferably in the morning.	
Packaging and labeling:	INCB054707 will be provided as [REDACTED] tablets, packaged in blister cards, and labeled as required per country requirement.	
Storage:	Ambient (15°C-30°C/59°F-86°F)	

6.2. Preparation, Handling, and Accountability

The investigator (or designee) is responsible for study treatment accountability, reconciliation, and record maintenance (ie, receipt, reconciliation, and final disposition records). Inventory and accountability records must be maintained and readily available for inspection by the study monitor and are open to inspection at any time by any applicable regulatory authorities. The investigator or designee must maintain records that document:

- Delivery of study drug to the study site.
- Inventory of study drug at the site.
- Participant use of the study drug including tablet counts from each supply dispensed.
- Return of study drug to the investigator or designee by participants.

The investigational product must be used only in accordance with the Protocol. The investigator will also maintain records adequately documenting that the participants were provided the specified study drug. These records should include dates, quantities, and any available batch or serial numbers or unique code numbers assigned to the investigational product and study participants.

Completed accountability records will be archived by the site. The investigator or designee will be expected to collect and retain all used, unused, and partially used containers of study drug until verified by the study monitor (unless otherwise agreed to by the sponsor). At the conclusion of the study, the investigator or designee will oversee shipment of any remaining study drug back to the sponsor or its designee for destruction according to institutional SOPs. If local procedures mandate on-site destruction of investigational supply, the site should (where local procedures allow) maintain the investigational supply until the study monitor inspects the accountability records in order to evaluate compliance and accuracy of accountability by the investigative site.

Further guidance and information for the final disposition of unused study treatments are provided in the Study Manual.

6.3. Measures to Minimize Bias: Randomization and Blinding

Randomization to treatment will occur centrally by IWRS (see Section 8.1.3). Full details will be provided in the IWRS Manual.

Participants, investigators, and the sponsor will be blinded to each participant's initial treatment assignment. Emergency unblinding will occur if an AE requires the investigator to be made aware of the participant's treatment assignment (see emergency unblinding procedures in Section 9.6).

6.4. Study Treatment Compliance

Compliance with all study-related treatments should be emphasized to the participant by the site personnel, and appropriate steps should be taken to optimize compliance during the study. Compliance with INCB054707 will be calculated by the sponsor based on the drug accountability documented by site personnel and monitored by the sponsor/designee using tablet counts. Participants will be instructed to bring all study drug with them to all study visits in order for site personnel to conduct tablet counts to assess study drug accountability. The drug accountability documentation will be used by the sponsor to calculate treatment compliance.

6.5. Dose-Limiting Toxicity and Determination of Maximum Tolerated Dose and/or Pharmacologically Active Dose

6.5.1. Definition of a Dose-Limiting Toxicity

Dose-limiting toxicity will be defined as the occurrence of any of the events listed in Table 7 occurring up to Week 8 (EOT), except those with a clear alternative explanation not related to study drug. All DLTs will be assessed for severity by the investigator using CTCAE v4.03 criteria. Participants who receive at least 1 dose of study drug at the level assigned or have a DLT will be considered evaluable for determining tolerability of the dose.

Table 7: Definition of Dose-Limiting Toxicity

Toxicity	Definition
Nonhematologic	
 Any liver function abnormalities that meet the definition of Hy's law.^a Any \geq Grade 3 nonhematologic toxicity EXCEPT: 
 Transient (\leq 72 hours) abnormal laboratory values without associated clinically significant signs or symptoms. Nausea, vomiting, and diarrhea adequately controlled with medical therapy within 48 hours. An event clearly associated with the underlying disease, disease progression, a concomitant medication, or comorbidity. Asymptomatic changes in lipid profiles.
Hematologic	
 Grade 2 neutropenia (neutrophils: 1 to $< 1.5 \times 10^9/L$) with \geq Grade 3 infection. \geq Grade 3 neutropenia (neutrophils: $< 1 \times 10^9/L$). \geq Grade 2 thrombocytopenia (platelets: $< 75 \times 10^9/L$). Grade 4 anemia (hemoglobin: $< 6.5 \text{ g/dL}$).
Events of special interest	
 Serious infections due to bacterial, mycobacterial, invasive fungal, viral, or other opportunistic pathogens; viral reactivation; malignancy.

^a Hy's law is defined as 1) ALT or AST elevation $> 3 \times \text{ULN}$, 2) total bilirubin $> 2 \times \text{ULN}$ without initial findings of cholestasis (elevated serum alkaline phosphatase), AND 3) no other apparent possible causes of aminotransferase elevation and hyperbilirubinemia, including, but not limited to, viral hepatitis, pre-existing chronic or acute liver disease, or the administration of other drug(s) known to be hepatotoxic.

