6.6.3. Criteria and Procedures for Dose Interruptions and Adjustments of Study Drug

Safety concerns should be discussed with the sponsor immediately upon occurrence or awareness to determine if the participant should continue or discontinue study treatment.

There are no dose modifications in this study. In some circumstances, it may be necessary to temporarily interrupt treatment with INCB054707 as a result of AEs or laboratory abnormalities that have an unclear relationship to the study drug (see [Table 8](#)). Except in cases of emergency, it is recommended that any laboratory findings be confirmed and that the investigator consult with the sponsor medical monitor (or other representative of the sponsor) before temporarily interrupting study drug. Participants who experience a recurrence of the AEs or laboratory abnormalities upon restarting the study drug may have the study drug permanently discontinued.

Table 8: Guidelines for Interrupting, Restarting, and Discontinuing Study Drug

ADVERSE EVENT	ACTION TAKEN
Chemistry	
AST and/or ALT $> 3.0 \times \text{ULN}$	
Step 1: Interrupt study drug administration up to 2 weeks (14 days) until the toxicity has resolved to $\leq 3.0 \times \text{ULN}$.
 
Step 2: Restart study drug, and monitor as described specifically in Section 9.3.

AST and/or ALT $> 5.0 \times \text{ULN}$	Discontinue study drug administration, and monitor as described specifically in Section 9.3.
Hematology	
Platelet counts 50 to $< 100 \times 10^9/\text{L}$ or $\geq 50\%$ decrease from baseline	
Step 1: Interrupt study drug administration up to 2 weeks (14 days) until the toxicity has resolved to $\geq 100 \times 10^9/\text{L}$.
 
Step 2: Restart study drug, and monitor as described in Section 9.3.

ANC 0.5 to $< 1.0 \times 10^9/\text{L}$	
Step 1: Interrupt study drug administration up to 2 weeks (14 days) until the toxicity has resolved to $\geq 1 \times 10^9/\text{L}$ or the baseline value.
 
Step 2: Restart study drug, and monitor as described specifically in Section 9.3.

Hemoglobin 8 to $< 10 \text{ g/dL}$ or $> 2 \text{ g/dL}$ decrease from baseline	
Step 1: Interrupt study drug administration up to 2 weeks (14 days) until the toxicity has resolved $\geq 10 \text{ g/dL}$ or $\leq 2 \text{ g/dL}$ decrease from baseline.
 
Step 2: Restart study drug, and monitor as described specifically in Section 9.3.

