
 Platelet count $< 50 \times 10^9/\text{L}$ ANC $< 0.5 \times 10^9/\text{L}$ ANC $< 1.0 \times 10^9/\text{L}$ with an oral temperature of at least 38.5°C OR with \geq Grade 3 infection Hemoglobin $< 8 \text{ g/dL}$ 	Discontinue study drug administration, and monitor as described specifically in Section 9.3.
Other toxicities	
Any Grade 1 or Grade 2 toxicity	Continue study drug and treat the toxicity; monitor as described specifically in Section 9.3.
Any Grade 3 toxicity except those defined in Table 7 (exception for any \geq Grade 3 nonhematologic toxicity)	
Step 1: Interrupt study drug up to 2 weeks (14 days), until toxicity resolves to \leq Grade 1.
 
Step 2: Restart study drug and monitor as described specifically in Section 9.3.

Any other Grade 4 toxicity	Discontinue study drug administration and follow-up as described in specifically Section 8.8.

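### Of the three blood counts in both tables, only hemoglobin has a permanent-stop level (<8 g/dL) milder than its DLT level (<6.5 g/dL), so a stop at 6.5 to <8 g/dL triggers neither DLT-based rule

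*Protocol*

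**What the plan says.** Protocol Table 7 (Section 6.5.1) lists the DLTs, which count up to Week 8 unless there is a clear alternative explanation unrelated to study drug. Its hematologic row includes "Grade 4 anemia (hemoglobin: $< 6.5 \text{ g/dL" and, for platelets, "Grade 2 thrombocytopenia (platelets: $< 75 \times 10^9/L". Neutrophils count below 1 x 10^9/L, or at 1 to <1.5 x 10^9/L with an infection of Grade 3 or higher. The general severity row is limited to events described as "Grade 3 nonhematologic toxicity EXCEPT", followed by a list of exceptions.

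Protocol Table 8 (Section 6.6.3) governs the individual participant. Drug is interrupted at "Hemoglobin 8 to $< 10 \text{ g/dL}$ or $> 2 \text{ g/dL}$ decrease from baseline". It is stopped for good at "Hemoglobin $< 8 \text{ g/dL", at "Platelet count $< 50 \times 10^9/\text{L", at ANC <0.5 x 10^9/L, and at ANC <1.0 x 10^9/L "with an oral temperature of at least 38.5°C OR with" an infection of Grade 3 or higher.

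Section 6.5.2 ties two rules to Table 7. A participant with a listed DLT attributed to study drug is unblinded for the SRC. Escalation ends if 3 or more INCB054707-treated participants in a cohort have DLTs. The same section leaves several matters to judgment: the SRC reviews each cohort's data blinded at Week 4, may ask for unblinded data, may wait for Week 8 and may recommend expanding the cohort. Escalation also ends if the drug is judged not tolerable, and teleconferences can adjudicate high-grade events as potentially dose-limiting.

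**The concern.** A permanent stop is the strongest action the protocol takes for one participant. For platelets and neutrophils, any value low enough to require it also counts toward the dose-level decision. For hemoglobin the order is reversed, so a participant can be taken off drug for anemia and add nothing to the DLT count.

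Safety is the trial's primary objective, and Section 10.1 names hemoglobin among the adverse events of interest. The consequence is confined to escalation. Anemia in the 6.5 to <8 g/dL band triggers neither DLT-based rule and reaches the dose decision only if someone chooses to act on it.

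Timing adds to this. The scheduled SRC review is at Week 4 and blinded, and the next cohort may open after it. Anemia that appears in Weeks 5 to 8 is still inside the DLT window but comes after that review.

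**Working it through.** **The plan's own figure.** Section 10.1 gives 9 active participants per dose level and more than an 85% chance of seeing at least one event at a 20% rate. 1 - 0.8^9 = 0.8658, which agrees. I use n = 9 below.

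**Is any permanent stop not a DLT?** Counts are x 10^9/L unless marked.

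| Count | Permanent stop (Table 8) | DLT (Table 7) | Stop that is not a DLT |
|---|---|---|---|
| Platelets | <50 | <75 | none |
| ANC | <0.5 | <1 | none |
| ANC with fever or Grade 3+ infection | <1.0 | <1 | none |
| Hemoglobin | <8 g/dL | <6.5 g/dL | 6.5 to <8 g/dL |

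The band is 8.0 - 6.5 = 1.5 g/dL wide. No other Table 7 row captures it: the general severity row is nonhematologic, and the special-interest row covers serious infections, viral reactivation and malignancy.

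**How far hemoglobin must fall.** Section 5.2 excludes hemoglobin <10 g/dL at screening. From 10 g/dL, the stop needs a fall of more than 10 - 8 = 2.0 g/dL and the DLT more than 10 - 6.5 = 3.5 g/dL. From an assumed 14 g/dL, the falls are 6.0 and 7.5 g/dL.

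**Effect on the 3-DLT rule.** The documents give no rate for this band, so every rate p is an assumption. With no other DLTs, the present rule gives a chance of 0. If the band counted, the chance per cohort would be

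P(X >= 3) = 1 - (1-p)^9 - 9p(1-p)^8 - 36p^2(1-p)^7.

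- p = 0.02: 1 - 0.8337 - 0.1531 - 0.0125 = 0.0006 from unrounded terms (0.001 to three decimals)
- p = 0.05: 1 - 0.6302 - 0.2985 - 0.0629 = 0.0084 (0.008)
- p = 0.10: 0.0530
- p = 0.20: 0.2618

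If other DLTs also occurred at an assumed 10%, in different participants so that the rates add, the present chance is 0.0530. Adding 2% gives 0.0833 (total 12%), and adding 5% gives 0.1409 (total 15%).

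**Effect on SRC unblinding.** The chance that at least 1 of 9 active participants has such an event, with no DLT-based unblinding following from it, is 1 - (1-p)^9: 0.1663 at 2%, 0.3698 at 5% and 0.6126 at 10%.

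**The case against.** The strongest reply is that the protocol never says a permanent stop must be a DLT. A stop protects one person, while a DLT counts toward a decision about a dose. Table 7 itself exempts transient laboratory values without significant signs or symptoms and asymptomatic lipid changes, so an isolated, short-lived ALT above 5 x ULN could end treatment without being a DLT. More than two rescue interventions (Section 8.2.4) also ends treatment. This stands as far as it goes: the reversed order is not a contradiction. But the Table 7 exemptions are written out as exceptions, and none covers anemia beyond the general one for a clear alternative explanation.

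The order may also be deliberate. The protocol singles out platelets for repeat testing, and Section 9.5 lists platelets and ANC, but not hemoglobin, as being of special interest. The dose justification and clinical risk text are not available to read, so it cannot be said that the sponsor had no reason.

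The judgment routes in Section 6.5.2 are real, and escalation is never automatic. What they lack is a trigger: none is set off by this event.

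On size, the objection is largely right. To reach the band, hemoglobin must fall past the interruption level (<10 g/dL, or a fall of >2 g/dL). Hematology is scheduled at Weeks 1, 2, 4, 6 and 8, and Weeks 3, 5 and 7 are added after a potentially clinically significant abnormality. The 10% and 20% rates have no basis for this band. No dose level follows the third cohort, so ending escalation matters only after the first two.

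A reader might also infer that the "Any other Grade 4 toxicity" stop in Table 8 opens the same gap for other cytopenias. Neither table gives a level for any other blood count, so the documents do not establish a comparable mismatch and the point is limited to hemoglobin.

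**Conclusion.** The point holds for hemoglobin alone. A value of 6.5 to <8 g/dL with no clear alternative cause ends treatment under Table 8, yet neither DLT-based rule in Section 6.5.2 responds to it. It can influence escalation only through SRC, sponsor or investigator judgment.

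The likely numerical effect on the escalation rule is small. With 9 active participants and no other DLTs, counting these events would move the chance of reaching 3 DLTs from 0 to 0.001 at 2% and 0.008 at 5%. It is larger if other DLTs are common. All of these rates are assumed.

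A reader might infer that participants with severe anemia are unprotected, or that the trial would misreport its safety results. The documents support neither. Table 8 interrupts and then stops drug at milder levels than the DLT. The SRC reviews each cohort before the next dose opens. The SAP (Sections 8.2.2 and 8.3.2) still tabulates treatment-emergent events leading to discontinuation and worst laboratory grades. This is an inexpensive tightening of a safety rule, not a flaw that undermines the trial.

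**What to change.** In Table 7, change the anemia criterion to hemoglobin <8 g/dL, stated by value because the table ties the Grade 4 label to <6.5 g/dL. Keep the exception for a clear alternative explanation. Every named permanent stop for the three blood counts would then also meet its DLT level.

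The cost is one table row in a protocol amendment. Hemoglobin is already measured in the scheduled hematology, so no visit, sample or data field is added. The downside is a slightly higher chance of ending escalation after a cohort that has a next dose level, at the sizes given above, and a few more participants unblinded to the SRC. Any extra halt would require active participants with anemia at the level where the protocol itself stops treatment.

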6.5.2. Procedures for Cohort Review and Dose Escalation

After all participants in each cohort have completed the Week 4 visit and assessments, a SRC will review safety data on a blinded basis from that cohort. If blinded data are determined to support the safety and tolerability of the dose for that cohort, the next higher dose cohort may open to enrollment. If necessary, the SRC may request to further review unblinded safety data from that cohort at Week 4. In the case that the unblinded data at Week 4 is not enough to support dose escalation, the SRC can also choose to wait until all participants complete Week 8 assessment and then make the decision. The SRC could also make a recommendation to expand a cohort to obtain additional safety data.

A participant's randomization will be unblinded for the SRC if the participant experiences any of the DLTs listed in [Table 7](#) and the DLT is attributed to study drug. If ≥ 3 participants in any cohort treated with INCB054707 have DLTs or the study drug is considered not tolerable, then the escalation will be terminated.

After the completion of a cohort, the sponsor may also be unblinded to safety and efficacy data from that cohort.

Telephone conferences will also be scheduled by the sponsor with active study investigators in order to review cohort-specific data and overall safety data, agree on dose escalation, adjudicate individual high-grade AEs as potentially dose-limiting, and guide other major study decisions.

6.6. Dose Modifications

6.6.1. Management of Dose-Limiting Toxicities or Other Urgent Situations

Investigators may employ any measures or concomitant medications necessary to optimally treat the participant after discussion with the sponsor (whenever possible).

6.6.2. Follow-Up of Dose-Limiting Toxicities

Any DLT should be monitored until it resolves to baseline or appears to have stabilized for a minimum of 2 weeks. During follow-up, participants should be seen as often as medically indicated to assure safety, in consultation with the medical monitor.

6.6.3. Criteria and Procedures for Dose Interruptions and Adjustments of Study Drug

Safety concerns should be discussed with the sponsor immediately upon occurrence or awareness to determine if the participant should continue or discontinue study treatment.

There are no dose modifications in this study. In some circumstances, it may be necessary to temporarily interrupt treatment with INCB054707 as a result of AEs or laboratory abnormalities that have an unclear relationship to the study drug (see [Table 8](#)). Except in cases of emergency, it is recommended that any laboratory findings be confirmed and that the investigator consult with the sponsor medical monitor (or other representative of the sponsor) before temporarily interrupting study drug. Participants who experience a recurrence of the AEs or laboratory abnormalities upon restarting the study drug may have the study drug permanently discontinued.

Table 8: Guidelines for Interrupting, Restarting, and Discontinuing Study Drug

ADVERSE EVENT	ACTION TAKEN
Chemistry	
AST and/or ALT $> 3.0 \times \text{ULN}$	
Step 1: Interrupt study drug administration up to 2 weeks (14 days) until the toxicity has resolved to $\leq 3.0 \times \text{ULN}$.
 
Step 2: Restart study drug, and monitor as described specifically in Section 9.3.

AST and/or ALT $> 5.0 \times \text{ULN}$	Discontinue study drug administration, and monitor as described specifically in Section 9.3.
Hematology	
Platelet counts 50 to $< 100 \times 10^9/\text{L}$ or $\geq 50\%$ decrease from baseline	
Step 1: Interrupt study drug administration up to 2 weeks (14 days) until the toxicity has resolved to $\geq 100 \times 10^9/\text{L}$.
 
Step 2: Restart study drug, and monitor as described in Section 9.3.

ANC 0.5 to $< 1.0 \times 10^9/\text{L}$	
Step 1: Interrupt study drug administration up to 2 weeks (14 days) until the toxicity has resolved to $\geq 1 \times 10^9/\text{L}$ or the baseline value.
 
Step 2: Restart study drug, and monitor as described specifically in Section 9.3.

Hemoglobin 8 to $< 10 \text{ g/dL}$ or $> 2 \text{ g/dL}$ decrease from baseline	
Step 1: Interrupt study drug administration up to 2 weeks (14 days) until the toxicity has resolved $\geq 10 \text{ g/dL}$ or $\leq 2 \text{ g/dL}$ decrease from baseline.
 
Step 2: Restart study drug, and monitor as described specifically in Section 9.3.


 Platelet count $< 50 \times 10^9/\text{L}$ ANC $< 0.5 \times 10^9/\text{L}$ ANC $< 1.0 \times 10^9/\text{L}$ with an oral temperature of at least 38.5°C OR with \geq Grade 3 infection Hemoglobin $< 8 \text{ g/dL}$ 	Discontinue study drug administration, and monitor as described specifically in Section 9.3.
Other toxicities	
Any Grade 1 or Grade 2 toxicity	Continue study drug and treat the toxicity; monitor as described specifically in Section 9.3.
Any Grade 3 toxicity except those defined in Table 7 (exception for any \geq Grade 3 nonhematologic toxicity)	
Step 1: Interrupt study drug up to 2 weeks (14 days), until toxicity resolves to \leq Grade 1.
 
Step 2: Restart study drug and monitor as described specifically in Section 9.3.

Any other Grade 4 toxicity	Discontinue study drug administration and follow-up as described in specifically Section 8.8.

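### Table 8's AST/ALT > 3.0 x ULN row lists restart on transaminases alone; adding an explicit Hy's law stop would be a cheap safety improvement

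*Protocol*

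**What the plan says.** **Protocol Section 6.6.3, Table 8.** When AST and/or ALT exceeds 3.0 x ULN, Step 1 is: "Interrupt study drug administration up to 2 weeks (14 days) until the toxicity has resolved to $\leq 3.0 \times \text{ULN". Step 2 is restart, with monitoring under Section 9.3. A separate row discontinues study drug above 5.0 x ULN. Both rows depend on transaminases only, and no Table 8 row names bilirubin or Hy's law. Restart is at the assigned dose: "There are no dose modifications in this study".

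**Protocol Section 6.5.1, Table 7.** The DLT list includes "Any liver function abnormalities that meet the definition of" Hy's law. The footnote requires ALT or AST > 3 x ULN, total bilirubin > 2 x ULN without initial cholestasis, and "no other apparent possible causes of aminotransferase elevation and hyperbilirubinemia".

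**Text around Table 8.** The table's title presents it as guidance. Section 6.6.3 opens with "Safety concerns should be discussed with the sponsor immediately upon occurrence or awareness to determine if the participant should continue or discontinue study treatment". It then describes temporary interruption as something that may be needed for events whose relationship to study drug is unclear.

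**DLT provisions.** Section 6.6.1 lets investigators use whatever measures are needed, after sponsor discussion where possible. Section 6.6.2 says "Any DLT should be monitored until it resolves to baseline or appears to have stabilized for a minimum of 2 weeks", with the medical monitor consulted. Section 6.5.2 provides for unblinding when a DLT is thought to be caused by the drug: "randomization will be unblinded for the SRC if the participant experiences any of the DLTs listed in" the DLT table. Section 7.1.1 makes withdrawal from treatment mandatory when the investigator judges that continuing would harm the participant.

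**The concern.** Tables 7 and 8 use the same transaminase threshold for different purposes. Above 3 x ULN, a raised bilirubin with no cholestasis and no other explanation turns an enzyme rise into a Hy's law case, and Table 7 recognises that. Table 8 does not separate the two situations. It offers one path, interrupt and restart, and the condition for leaving it is an enzyme value that says nothing about bilirubin.

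If a site follows the row and no general safeguard intervenes, a participant is re-exposed at the full assigned dose after a combined transaminase and bilirubin rise with no other apparent cause. Safety is the trial's primary objective, and Section 10.1 names liver function among the adverse events of interest, so it is reasonable to expect the dosing table to say what happens here.

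**Working it through.** **The plan's own figure.** Section 10.1 gives 9 participants per dose level and a 20% event rate. The chance of at least one event is 1 − 0.8^9 = 1 − 0.134 = 0.866, which agrees with the stated > 85%. The point below does not depend on this figure.

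**Thresholds side by side.** Take a participant with total bilirubin > 2 x ULN, no initial cholestasis and no other apparent cause.

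| Peak AST/ALT | Table 7 | Table 8 AST/ALT rows |
|---|---|---|
| ≤ 3.0 x ULN | not Hy's law | no row |
| > 3.0 to 5.0 x ULN | Hy's law, a DLT | interrupt up to 14 days, restart at ≤ 3.0 x ULN |
| > 5.0 x ULN | Hy's law, a DLT | discontinue |

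The gap is the middle band.

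**Does another provision close it?**
- Section 6.5.2: SRC unblinding for a DLT attributed to study drug, and an end to escalation at 3 or more DLTs on active drug in a cohort. Neither stops the individual participant.
- Sections 6.6.1 and 6.6.2: management and follow-up, with no required stop.
- Section 7.1.1: a required stop, but triggered by judgment and not by a hepatic criterion.
- Section 9.3, to which the row points: general adverse event recording and follow-up, with no hepatic rule.
- Table 8, other toxicities: a Grade 4 event is discontinued. The Grade 3 row ends in restart, and its exception referring to Table 7 is hard to read. The documents give no bilirubin limits for these grades, so it cannot be said which row a given bilirubin value would reach.

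**Does DLT status itself imply a stop?** No. Table 7 makes platelets < 75 x 10^9/L and neutrophils < 1 x 10^9/L DLTs, yet Table 8 lists interruption and restart for platelets 50 to < 100 and ANC 0.5 to < 1.0. If a stop is intended for Hy's law, it has to be written.

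**Illustration (assumed values).** AST/ALT is 4 x ULN with bilirubin 2.5 x ULN, no cholestasis and no other cause. By day 10 AST/ALT is 2.9 x ULN and bilirubin is unchanged. Since 2.9 ≤ 3.0 and 10 ≤ 14 days, the row's restart condition is met, while the DLT has neither returned to baseline nor been stable for 2 weeks and so remains under Section 6.6.2 follow-up. This assumes that the bilirubin rise is not graded high enough to bring in another row.

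**Exposure.** From Section 4.1: 3 cohorts x 9 = 27 active participants; 27 x 8 weeks = 216 participant-weeks; 216 / 52.18 = 4.1 participant-years. The documents give no rate for such events.

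**The case against.** The best counter-argument is the scope sentence in Section 6.6.3. Interruption is described for events of unclear relationship to study drug, whereas Hy's law requires that no other cause be apparent. A confirmed case therefore fits the interrupt-and-restart row poorly, and the row may never have been meant for it. That has force, but it does not close the gap. The row does not repeat the limit. A site will often enter the row before other causes have been excluded, when the relationship is still unclear. And if confirmed cases fall outside the row, Table 8 specifies no action for one peaking at > 3.0 to 5.0 x ULN.

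The second argument is that several safeguards would have to fail together: sponsor discussion, DLT management and follow-up with the medical monitor, and the investigator's duty under Section 7.1.1. This stands as a limit on the weight of the point. These provisions work case by case, and none names bilirubin or Hy's law.

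A reader might also infer that Table 8 tells sites to keep dosing through a moderate bilirubin rise, because the Grade 1 or 2 row says "Continue study drug and treat the toxicity". The documents do not support this. That row sits under other toxicities while the participant is already in the chemistry interruption row, and the reading needs bilirubin grade limits that the documents do not give.

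**Conclusion.** The point holds as a cheap safety improvement. The > 3.0 x ULN row lists restart on a transaminase value alone, and no visible provision requires study drug to be stopped for a Hy's law case peaking at > 3.0 to 5.0 x ULN.

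A reader might go further and infer that the protocol compels restart after Hy's law, or that Tables 7 and 8 contradict each other. Neither follows. Table 8 is guidance set within a sponsor discussion about continuing or stopping. Nothing in the documents says that a DLT, or Hy's law in particular, must end treatment, and other DLTs may also be restarted. That Hy's law should end treatment is a recommendation on safety grounds, not a rule that the protocol breaks.

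With about 4.1 active participant-years planned, such a case would be rare; the argument is its severity. No sample size, endpoint or analysis is affected. The conclusion rests on the visible text. Tables 7 and 8 are legible on this point, but the potential-risks table (Table 4) and the analyte list (Table 11) are not visible, so hepatic guidance there cannot be ruled out.

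**What to change.** 1. Add a Table 8 row: AST and/or ALT > 3.0 x ULN with total bilirubin > 2 x ULN, meeting the Table 7 Hy's law definition – permanently discontinue study drug.
2. Add to the existing > 3.0 x ULN row: except cases meeting Hy's law.
3. State that study drug is held while alternative causes are assessed, and that the existing row applies if another cause is established.

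Table 8 already contains a combined stop of this kind: ANC < 1.0 x 10^9/L together with fever or an infection of Grade 3 or higher.

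The cost is amendment wording. Total bilirubin is already needed to apply Table 7, so no new test is expected, although the analyte list could not be checked. The downside is that a rare participant who might have tolerated restart stops treatment early.
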